5.4 Analysis Visit Windows

In general, the OL Baseline assessment is defined as the last non-missing, including those from repeated and unscheduled measurements, within 30 days before the first OL dose date or on the first OL dose date. Exceptions to this definition will be handled on a case-by-case basis.

Efficacy and safety assessments will be summarized by analysis visit as presented in Table 2 below.

Table 2 Analysis Visit Windows

Open-label (OL) Analysis Visit Name	Target Study Day ¹	Study Day Interval
OL Baseline	1	≤1 (based on the first OL dose date)
OL Week 2	15	2 to 21
OL Week 4	29	22 to 42
OL Week 8	57	43 to 70
OL Week 12	85	71 to 98
OL Week 16	113	99 to 154
OL Week 28	197	155 to 238
OL Week 40	281	239 to 322
OL Week 52	365	323 to 379
Follow-up	395	380 to maximum

¹ If the assessment date ≥ first OL dose date, study day = assessment date - first OL dose date + 1, otherwise study day = assessment date – first OL dose date. Study day 1 is the first OL dose date.

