3.1.1 Open-label Treatment Period (52 Weeks)

Eligible subjects will begin pimavanserin once-daily dosing at 34 mg.

Dose adjustments of pimavanserin down to 20 mg and up to 34 mg are permitted at any study visit (scheduled or unscheduled) after Baseline based on Investigator assessment of clinical response.

During the Treatment period, clinic visits will be conducted at Baseline and Weeks 2, 4, 8, 12, 16, 28, 40, and 52 (EOT), or upon early termination from the study.

Study drug will be dispensed to the subject to take home at the Baseline visit. The subject and study partner/caregiver will be provided instructions to take the first dose of study drug on the day after the Baseline visit.

All concomitant permitted medications should remain stable during the study but can be adjusted or discontinued, if clinically appropriate. These changes should be discussed with the Medical Monitor or designee as appropriate.

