3 STUDY DESIGN

3.1 General Study Design

The ACP-103-047 study is a Phase 3b, open-label (OL) extension study to evaluate the long-term safety and tolerability of pimavanserin in adult and elderly subjects with neuropsychiatric symptoms related to neurodegenerative disease. This study will be conducted as a 52-week OL extension of the ACP-103-046 study (antecedent study), consisting of two periods: a 52 week OL treatment period, and a 4 week safety follow-up period. The total duration of exposure to pimavanserin may be greater than 52 weeks as subjects may have been treated with pimavanserin in the antecedent study. Approximately 100 global sites will participate in this study.

Eligible subjects will be those subjects who completed the ACP-103-046 study and, in the Investigator's judgement, may continue to benefit from longer term therapy with pimavanserin. Subject and study partner/caregiver consent for the present study must be obtained prior to the final procedures being performed at the antecedent study's end of treatment (EOT or early termination (ET) visit (if the study was ended early by the Sponsor). Data from the EOT/ET procedures of the antecedent study will be transferred over to the ACP-103-047 study for inclusion as baseline information, and this antecedent EOT visit will be considered the Baseline visit (Visit 1).

Eligible subjects will receive once daily doses of pimavanserin during the treatment period, starting with 34 mg of pimavanserin at the Baseline visit. Dose adjustments of pimavanserin down to 20 mg and up to 34 mg are permitted at any study visit (scheduled or unscheduled) after Baseline.

During the Treatment Period, clinic visits will be conducted at Baseline and Weeks 2, 4, 8, 12, 16, 28, 40 and 52 (EOT), or upon ET from the study.

[figure not shown]
Study drug will be dispensed to the subject to take home at the Baseline visit and at each subsequent visit (with the exception of Week 52). The subject and their study partner/caregiver will be provided instructions to take the first dose of study drug on the day after the Baseline visit. It is recommended that the subject take the study drug at approximately the same time each day as a single, oral dose.

All concomitant permitted medications should remain stable during the study but can be adjusted or discontinued, if clinically appropriate. These changes should be discussed with the Medical Monitor or designee as appropriate.

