14.1 Adverse Events

All AEs, classified by preferred term, will be coded using MedDRA version 23.0 or newer.

An AE (classified by PT) will be considered a TEAE if it started on or after the OL first dose of study drug and no later than the OL last dose date + 30. AEs reported on Day 1 based on pre-dose findings will not be considered as TEAEs.

For the following summaries, the event counts and the number and percentage of subjects reporting TEAEs will be tabulated by cohort and overall:

- TEAEs by SOC and PT
- Most frequently reported TEAEs by SOC and PT
 - PTs reported by $\geq 5\%$ and $\geq 2\%$ (overall) of subjects in the Safety Analysis Set
- TEAEs by PT
- TEAEs by SOC, PT, and maximum severity
 - if more than 1 AE occurs with the same PT for the same subject, the subject will be counted only once for that PT using the most severe occurrence
- TEAEs related to study drug by SOC and PT
- Treatment-emergent serious adverse events (TESAEs) by SOC and PT
- TEAEs leading to discontinuation of study drug by SOC and PT
- AEs with fatal outcome by SOC and PT
- TEAEs with fatal outcome (that occurred within 30 days of last dose) by SOC and PT

For tabulations that include SOC and PT the display will be sorted alphabetically by SOC and then by descending subject frequency for the PTs based on counts in the Safety Analysis Set within each SOC. SOCs will not be included in the TEAEs by PT tabulation. This display will be sorted by descending subject frequency based on counts in the Safety Analysis Set.

An AE listing by subject will display all events, including those which are not TE, and will include the verbatim term in addition to the MedDRA SOC and PT. This listing will also include all relevant eCRF data associated with the event: e.g. date of onset, dose level at date of onset, date resolved, date of the first and last dose of study drug, severity, frequency, outcome, relationship to study drug, action taken with study drug, and required therapy. When a date is presented, the study day associated with the date will also be displayed. Separate listings will be presented for subjects with SAEs, subjects with AEs leading to discontinuation and subjects who died (if any). In these listings, an indicator for TEAEs will also be included.

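### OL Baseline has no pre-dose condition, so a post-dose value on the first dose date can replace Visit 1 and leave the tables referenced to OL Baseline

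*SAP*

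**What the plan says.** SAP 5.4 defines the OL Baseline as the last non-missing assessment, "including those from repeated and unscheduled measurements, within 30 days before the first OL dose date or on the first OL dose date". Table 2 gives the interval for OL Baseline as "≤1 (based on the first OL dose date", with Day 1 as target, and starts OL Week 2 at Day 2. The table footnote fixes the scale: "Study day 1 is the first OL dose date". The only safeguard is "Exceptions to this definition will be handled on a case-by-case basis".

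Protocol 3.1.1 instructs the subject to "take the first dose of study drug on the day after the Baseline visit". SAP 3.1 also gives "instructions to take the first dose of study drug on the day after the Baseline visit", but elsewhere in the same section describes subjects as "starting with 34 mg of pimavanserin at the Baseline visit".

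For adverse events, SAP 14.1 does separate the two halves of Day 1: "AEs reported on Day 1 based on pre-dose findings will not be considered as TEAEs".

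**The concern.** When the first dose follows Visit 1 by a day, the scheduled Baseline lies on Day -1 and the next scheduled visit is Week 2. Any other assessment dated Day 1 is unscheduled, repeated or late, and it may have been made after dosing. The stated rule prefers that value to Visit 1 because it is later, and it contains no test of whether the drug had already been taken.

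A post-treatment value would then serve as the reference for all later changes from OL Baseline, and would not itself be examined as an on-treatment finding in those tables. If the value is abnormal, the error runs towards understating harm, in a study whose primary objective is safety. For Cohort 1 (placebo in the antecedent study), Day 1 is the first exposure to pimavanserin in the two studies.

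**Working it through.** **1. Which value is selected.** Study day is date - first dose date + 1 on or after the first dose, and date - first dose date before it (Table 2 footnote).

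| Assessment | Study day | Table 2 window |
|---|---|---|
| Visit 1, day before first dose | -1 | OL Baseline |
| Unscheduled, on first dose date, after the dose | 1 | OL Baseline |
| Following day | 2 | OL Week 2 |

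Both selection rules choose Day 1 over Day -1. It is the later value (SAP 5.4), and it sits on the target day (SAP 5.4.2 takes the value nearest the target).

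**2. What can be recorded that day.** Protocol 6.5 and Table S-1 list vital signs, CGI-S, ESRS-A and C-SSRS or GCAS at unscheduled visits. ECG and laboratory tests are not on that list and would be done only as additional evaluations.

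**3. Where the value drops out.**
- *Change from OL Baseline:* the Day 1 value becomes the reference.
- *Vital-sign PCI on OL Baseline (SAP 14.3.2, Table 7):* for blood pressure and pulse, a PCI value must be post-baseline and meet both an absolute limit and a change. A value filed as Baseline cannot qualify.
- *ECG (SAP 14.4.2):* the overall post-Baseline maximum and overall PCI summaries cover the OL period only.
- *C-SSRS and GCAS (SAP 14.6.3):* only post-OL Baseline findings are tabulated, for the OL period only. Later assessments ask about the time since the previous visit, so Week 2 need not pick the finding up again. It would appear among the Baseline characteristics of SAP 8.2.

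**4. Where it survives.** All assessments are listed (SAP 5.4.1). Laboratory values and absolute ECG values that are PCI at Baseline still trigger the PCI listings (SAP 14.2.5.3, 14.4.2.4). A post-dose event is still a TEAE (SAP 14.1). Changes from the double-blind (DB) Baseline, and the laboratory and vital-sign PCI tables across both studies, can still include the value (SAP 5.2, 14.2.5.3, 14.3.2).

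**5. Illustrations. All measurements are assumed; the criteria are from SAP Tables 7 and 8.**

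Systolic pressure: Visit 1 130, Day 1 post-dose 88, Week 2 125 mmHg.

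| | As written | Visit 1 as Baseline |
|---|---|---|
| OL Baseline | 88 | 130 |
| Low PCI on Day 1 | cannot be counted | 88 ≤ 90 and 130 - 88 = 42 ≥ 20: counted |
| Week 2 change | 125 - 88 = +37 | 125 - 130 = -5 |

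In the table across both studies, 88 would still count as PCI if the DB Baseline were at least 88 + 20 = 108.

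QTcF in msec, Visit 1 value 430:

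| Day 1; later values | Largest change as written | Largest change from Visit 1 |
|---|---|---|
| 495; 470, 465 | 470 - 495 = -25, not >60 | 495 - 430 = +65, PCI |
| 450; 495 | 495 - 450 = +45, not >60 | 495 - 430 = +65, PCI |

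In the second row the Day 1 value is itself unremarkable, yet as Baseline it hides a later change.

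**6. Effect on group summaries.** One subject like the systolic example shifts the sum of Week 2 changes by 37 - (-5) = 42 mmHg. With the 353 subjects in the second interim analysis (SAP 16.1), the mean moves by 42/353 = 0.12 mmHg and the PCI percentage by 1/353 = 0.28 points. If the two cohorts were of equal size (assumed), the cohort figures would be twice these: about 0.24 mmHg and 0.57 points.

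**The case against.** The case against has several parts, and much of it stands.

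- A reader might infer that the value is lost as a safety finding, or can never count as post-Baseline. The documents do not support that, for the reasons in step 4 of the working. The rescue is partial, however. The overall ECG and suicidality tables have no counterpart across both studies. The vital-sign PCI listing nominally includes Baseline, but the two-part Table 7 criteria leave a blood pressure or pulse value filed as OL Baseline with no change to qualify on.
- The situation is rare. It needs an extra assessment on the first dose date, after the dose. Unscheduled visits are at the investigator's discretion, so one cannot assume that something had gone wrong. No hypothesis is tested, and the effect on group means is negligible.
- Including the first dose date has a purpose. If a subject is assessed and dosed on the same day, which one phrase in SAP 3.1 could suggest, that date is needed to keep the Visit 1 value. This argues for adding a pre-dose condition, not for dropping the date.
- A reader might call the TEAE rule the opposite convention. That goes too far, since event onset and baseline selection are different questions. The comparison shows only that the SAP recognises the pre-dose distinction on Day 1 and does not carry it over to assessments.
- SAP 5.4 begins with a general qualifier, and SAP 5.4.2 refers to a separate programming conventions document, which may hold a pre-dose rule. The SAP states no criterion, and case-by-case decisions would be made with open-label data in view.

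**Conclusion.** The gap is real and modest. As written, SAP 5.4, Table 2 and SAP 5.4.2 all make a post-dose Day 1 value the OL Baseline in place of Visit 1. The consequence is confined to summaries referenced to OL Baseline: change from Baseline, vital-sign PCI, overall ECG maximum and PCI, and the OL-only C-SSRS and GCAS tables. For a subject affected, the error can reverse the sign of later changes and remove a PCI count. Across the study it is small.

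This rests on three assumptions: the first dose follows Visit 1 by a day, some subjects have an assessment on the first dose date after dosing, and no unseen programming rule already excludes such values. The number of affected subjects is not in the documents and is probably low. The point merits correction because rare acute findings are what the worst-value and suicidality tables are meant to show.

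**What to change.** In SAP 5.4, define OL Baseline as the last non-missing value before the first OL dose, keeping the 30-day limit, and add:

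- A value dated on the first dose date is accepted only if it comes from Visit 1 or is documented as pre-dose.
- A value on that date documented as post-dose is post-Baseline.
- If the timing of a value on that date from outside Visit 1 is unknown, the Visit 1 value stays as Baseline. The Day 1 value counts as post-Baseline in the overall worst-value, PCI and suicidality summaries, and is flagged in the listing.

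Amend the OL Baseline row of Table 2 to match. The OL Week 2 row can stay as it is if the text says that post-dose Day 1 values enter the overall summaries only. Reconcile the two statements in SAP 3.1 about the day of the first dose; the rule above works under either.

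The cost is a few sentences and one table row. The rule can rest on visit labels and dates, so it does not depend on a recorded dose time, which the documents do not show is collected for doses taken at home. There is one small downside: an untimed value that was in fact pre-dose could be counted as post-Baseline. The flag makes such cases visible. A listing of non-Visit 1 assessments dated on the first dose date would show how many subjects are involved.

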5.4.1 Unscheduled Assessments

Both scheduled and unscheduled assessments, including early termination visits, will be considered for planned timepoint summaries. All assessments will be presented in data listings.

5.4.2 Multiple Measurements within Visit Windows

If more than one assessment falls within a given window then the assessment closest to the target study day will be selected for the by-visit summaries. If two assessments are equidistant from the target day then the chronologically last assessment will be used for summary. Exceptions may be made for incomplete assessments, in which case, more complete assessments may be given priority. Details are provided in a separate programming conventions document.

For safety summaries where the most extreme values should be selected, e.g. overall post-OL Baseline minimum, and overall post-OL Baseline maximum, all non-missing post-OL Baseline values should be considered, regardless of whether the value is selected for the by-visit summaries. All results will be presented in data listings.

When replicate ECGs are collect at a given timepoint (typically, in triplicate), the average of the replicate values (i.e., PR interval, QRS duration, QT interval, QTcB interval, QTcF interval, and RR interval) will be considered as one assessment for the analyses.

5.5 Data Handling Conventions

5.5.1 Missing or Incomplete Date for Last Dose of Study Drug

In the Safety Analysis Set, if the last dose date of study drug is missing for a subject who completed or early terminated from the study, then the date of the end-of-study/early termination visit will be used in the calculation of treatment duration. For the incomplete last dose date of the study drug, the imputation algorithms will be detailed in the analysis dataset specification document. The missing or incomplete dates will be displayed in the data listings as reported on the eCRF rather than the imputed dates.

For any data summarization before final database lock, if a subject is still ongoing, then the last dose date will be imputed using the database extract date.

5.5.2 Missing or Incomplete Dates for Concomitant or Post-Treatment Medications

Missing or incomplete medication start or end dates will be imputed for the purpose of determining whether the medications are taken concomitantly (see [Section 10](#) for definition). When the chronological order of medication use relative to the study drug treatment period is unclear due to missing or incomplete date(s), the medication will be considered as concomitant. The imputation algorithms will be detailed in the analysis dataset specification document. The missing or incomplete dates will be displayed in the data listings as reported on the eCRF rather than the imputed dates.

5.5.3 Missing or Incomplete Dates for Adverse Events

Missing or incomplete AE start dates will be imputed for the purpose of determining whether the AEs are TE (see [Section 14.1](#) for definition). When the chronological order of an AE onset relative to the study drug treatment period is unclear due to missing or incomplete date(s), the AE will be considered as TE. The imputation algorithms will be detailed in the analysis dataset specification document. The missing or incomplete dates will be displayed in the data listings as reported on the eCRF rather than the imputed dates.

5.5.4 Missing Severity Assessment for Adverse Events

If the severity is missing for a TEAE a severity of “Severe” will be assigned. The imputed values for severity assessment will be used for incidence summaries, and the actual (missing) values will be presented in data listings.

5.5.5 Missing Relationship to Study Drug for Adverse Events

If the relationship to study drug is missing for a TEAE, a causality of “Related” will be assigned. The imputed values for relationship to study drug will be used for incidence summaries, and the actual (missing) values will be presented in data listings.

5.5.6 Character Values of Clinical Laboratory Variables

If the reported value of a clinical laboratory variable cannot be used in a summary due to, for example, a character string reported for a numeric variable, an appropriately determined coded value will be used in the summary. The coding algorithms will be detailed in the analysis dataset specification document. The actual values as reported in the database will be presented in data listings.

6 SUBJECT ENROLLMENT AND DISPOSITION

The number of sites that enrolled at least 1 subject and the number of subjects enrolled will be summarized by region (North America, Europe, and rest of world) and overall. For enrolled subjects, the number and percentage of subjects in the Safety Analysis Set will be summarized by region (North America, Europe, or rest of world). A listing will be provided displaying all subjects excluded from the Safety Analysis Set (if any), and will include reason(s) for exclusion.

The number and percentage of subjects who completed or discontinued (all discontinued and by discontinuation reason) the study will also be summarized by region and overall for the Safety Analysis Set. Early terminations of subjects due to COVID-19 related reasons will be captured in the eCRFs and summarized.

7 PROTOCOL DEVIATIONS

Protocol deviations that occur during Study ACP-103-047 will be reviewed periodically over the course of the study. The review process, definition of the deviation categories, and the classification of a deviation as major or minor will be detailed in the Protocol Deviation Management Plan. Protocol deviations will also be assessed with respect to relationship to COVID-19.

For enrolled subjects, a summary of the number and percentage of subjects with major protocol deviations for each deviation category will be presented in three ways: all protocol deviations, COVID-19 related protocol deviations, and non COVID-19 related protocol deviations.

Similarly, three data listings of major protocol deviations will be provided: All deviations, COVID-19 related protocol deviations, and non COVID-19 related protocol deviations. Additionally, a data listing of all minor COVID-19 related protocol deviations will be provided.

A listing of protocol deviations will also be presented in three ways as described above.

8 DEMOGRAPHICS AND OTHER BASELINE CHARACTERISTICS

Demographics and OL Baseline characteristics will be summarized using descriptive statistics. Summaries by region (North America, Europe, or rest of world) will also be presented.

8.1 Demographics

Demographic variables include age, sex, primary race (subjects of multi-racial background can only identify/select one primary race on eCRF, or choose “other” and specify), ethnicity, height, weight, body mass index (BMI), region, subject living situation, and partner/caregiver relationship.

The reported age reflects a subject’s age at the OL Baseline visit date. Age and BMI will be presented as both continuous and categorical variables. Age categories will be presented as <65, 65 to 74, 75 to 84, and ≥ 85 years old. BMI categories (kg/m^2) will be presented as <25, 25 to 30, and >30.

8.2 Disease Characteristics and Neuropsychiatric History

Disease characteristics at OL Baseline will be summarized using descriptive statistics. MMSE total score, CGI-S, EQ-5D-5L VAS, SDI total score, and ESRS-A total score will be presented as continuous variables. In addition, CGI-S will be presented as a categorical

variable using categories of 1 to 7, and MMSE will be presented as a categorical variable using categories of ≤ 10 , 11 to 17, 18 to 24, and 25 to 30. For the C-SSRS the number and percentage of subjects having suicidal ideation or behavior since the last visit will be presented. For the GCAS, the number and percentage of subjects within each rating since the last visit (absent, feels life is not worth living, wishes he/she were dead or any thoughts of possible death to self, suicidal ideas or gestures, and attempts at suicide) will be presented.

Neuropsychiatric history will be summarized descriptively for continuous and categorical variables. The OL Baseline visit date will be used as the reference date for calculation of durations. For both the Disease Characteristics and Neuropsychiatric History, summaries by region (North America, Europe, and rest of world) will also be presented. The Neuropsychiatric history will be pushed into the -047 database from the -046 study. If there have been any changes in the subject's neuropsychiatric history since completing this form for the -046 study, appropriate updates should be made by editing the affected fields.

